### 8.2.2 Adjusted Inflammatory Neuropathy Cause and Treatment (INCAT) and CIDP relapse

The INCAT disability scale is a 10-point clinician-reported ordinal measure capturing problems in daily arm and leg activities and mobility. The measure captures daily activities such as dressing the upper part of the body, doing and undoing buttons and zips, washing and brushing hair, and handling coins. Each item is scored as being “not affected”, “affected but not prevented”, or “prevented”. The leg scale measures problems with walking, taking into account the use of aids.

The investigator (or qualified personnel) will record the participant's INCAT arm and leg disability score at each scheduled assessment.

The INCAT score is the sum of the eCRF-captured arm disability classification (from 0 to 5) and leg disability classification (from 0 to 5). The INCAT scale ranges from 0 (no signs of disability) to 10 (most severe disability score).

If there is only one point deterioration/improvement in the participant's upper limb score (arm disability score) ie, from 0 (normal) to 1 (minor symptoms) or from 1 to 0, this difference should not be considered as a significant worsening/improvement and the related difference between baseline and the respective visit should be ignored when evaluating the adjusted INCAT score for the visit in the following way:

For each visit's INCAT score, the adjusted INCAT is

- (a) adjusted INCAT score = INCAT score - 1, if the arm disability score for this participant is 0 at baseline and 1 at the respective visit
- (b) adjusted INCAT score = INCAT score +1, if the arm disability score for this participant is 1 at baseline and 0 at the respective visit
- (c) adjusted INCAT score = INCAT score in any other case.

	Baseline score	Visit score	Total adjusted INCAT score
Arm disability score	0	1	Total adjusted INCAT score = Total visit INCAT score - 1
	1	0	Total adjusted INCAT score = Total visit INCAT score + 1
	Any other case		No adjustment

CIDP relapse (adjusted Inflammatory Neuropathy Cause and Treatment, INCAT) is defined as an increase from Baseline of at least 1 point in the adjusted INCAT score.

Values and changes from Baseline in adjusted INCAT score will be summarized by treatment group and for all participants and listed by treatment group at each scheduled assessment during the Treatment and Observation Period. For the change from Baseline at each scheduled assessment during the Treatment and Observation Period, treatment differences will be compared using the same MMRM analysis as for the primary endpoint, with the fixed categorical effects of treatment group, assessment week (at pre-specified levels determined by the visit schedule), the treatment by week interaction and the route of administration of prior Ig therapy, as well as continuous fixed covariate of the Baseline value and participant as a random effect. Analyses will be performed for the FAS utilizing the observed cases and repeated for the PPS.

INCAT score measurements will be listed by treatment group.

The statistical methods applied to CIDP relapse (adjusted INCAT) and time to CIDP relapse (adjusted INCAT) will be the same as for CIDP relapse (iRODS), see Sections [8.2.1](#) and [8.2.1.1](#).

The rule for handling missing data is described in Section [4.2.1](#).

Mean change from Baseline in adjusted INCAT score, including 90% CI will be plotted against timepoint for both treatments.

### **8.2.3 Maximum grip strength as assessed by site personnel and CIDP relapse**

Grip strength is assessed by qualified site personnel each scheduled assessment. Qualified site personnel will be trained regarding obtaining and recording measurements. At each

scheduled visit, the grip strength, generated by the participant, and measured using a standardized tool, will be evaluated 3 times in the dominant hand. All 3 assessments will be recorded in the eCRF. For analyses, UCB will utilize the maximum of the 3 assessments. Efficacy will be assessed as change from Baseline in maximum grip strength score at each scheduled assessment by treatment group during the Treatment and Observation Periods.

CIDP relapse (maximum grip strength as assessed by site personnel) is defined as a clinically important deterioration from Baseline in grip strength as measured by site personnel, ie, a decline of  $>14\text{kPa}$ .

Values and changes from Baseline in maximum grip strength score taken by site personnel will be summarized by treatment group and for all participants and listed by treatment group at each scheduled assessment during the Treatment and Observation Period.

For the change from Baseline in maximum grip strength at each scheduled assessment during the Treatment and Observation Period, treatment differences will be compared using the same MMRM analysis as for the primary endpoint, with the fixed categorical effects of treatment group, assessment week (at pre-specified levels determined by the visit schedule), the treatment by week interaction and the route of administration of prior Ig therapy, as well as continuous fixed covariate of the Baseline value, and participant as a random effect.

Analyses will be performed for the FAS utilizing the observed cases and repeated for the PPS.

Values of grip strength score taken by site personnel will be listed by treatment group. All 3 assessments taken at the scheduled assessments will be listed and the maximum per scheduled assessment will be flagged.

The statistical methods applied to CIDP relapse (maximum grip strength as assessed by site personnel) and time to CIDP relapse (maximum grip strength as assessed by site personnel) will be the same as for CIDP relapse (iRODS), see Sections 8.2.1 and 8.2.1.1. The rule for handling missing data is described in Section 4.2.1.

The analyses on CIDP relapse and time to CIDP relapse will be repeated with a CIDP relapse definition based on a decline of  $>8\text{kPa}$ .

Mean change from Baseline in maximum grip strength score, including 90% CI will be plotted against timepoint for both treatments.

#### **8.2.4 Patient-reported grip strength**

During the study, participants keep e-diaries to record daily grip strength from the Screening Visit until the end of study participation. Participants should be reminded to bring their diaries with them to each clinic visit and to have them available at home nursing visits. Participants will be trained by the site personnel and receive a manual describing how to assess grip strength using a standardized tool. At approximately the same time every day, the maximum grip strength, the peak pressure generated by the participant, will be assessed 3 times, with at least 30sec between measurements, using the dominant hand. Participants will be asked to complete their diaries each day and record the values for each of the 3 assessments.

For the purpose of the analysis, the mean of the maximum of the 3 daily assessments taken during the last three non-missing days prior to the scheduled visit will be used. Missing data will be handled as described in Section 4.2.1.

Values and changes from Baseline in mean daily maximum grip strength score taken by the participant will be summarized by treatment group and for all participants and listed by

treatment group at each scheduled visit during the Treatment and Observation Period. The treatment differences of change from baseline in the derived grip strength score will be compared using the same MMRM analysis as for the primary endpoint, with the fixed categorical effects of treatment group, assessment week (at pre-specified levels determined by the visit schedule), the treatment by week interaction and the route of administration of prior Ig therapy, as well as continuous fixed covariate of the Baseline value, and participant as a random effect. Analyses will be performed for the FAS utilizing the observed cases and repeated for the PPS.

Values of grip strength score taken by the participant as well as derived scores will be listed by treatment group. All 3 daily assessments taken at the scheduled assessments will be listed and the maximum per scheduled assessment will be flagged.

In addition to the above the daily maximum values will be displayed graphically over time, i.e. each treatment group's mean value and 90% CI of the maximum of the participants' three daily grip strength measurements will be displayed versus the relative day.

#### **8.2.5 CIDP relapse**

The event of CIDP relapse is defined by occurrence of either relapse across the 3 calculated criteria: iRODS relapse, adjusted INCAT relapse and maximum grip strength as assessed by site personnel (14 kPa) relapse as defined in sections 8.2.1, 8.2.2 and 8.2.3 and 'other' as captured in the CRF by the investigator. It will be described and analysed in the same way as the individual relapse definitions. This will be done for the FAS and the PPS.

#### **8.2.6 RT-MRC sum score**

The RT-MRC sum score is a summation of the RT-MRC grades in integers of the following muscles on each side: upper arm abductors, elbow flexors, wrist extensors, hip flexors, knee extensors, and foot dorsal flexors.

The RT-MRC sum score was developed based on a Rasch analysis of the original MRC grading system ([Me10]; [Me02]; [Va12]). The original MRC sum score grades from 0 to 5 (0 = No movement, no contraction; 1 = Visible contraction without movement; 2 = Movement, but only with gravity eliminated; 3 = Movement against gravity; 4 = Movement against resistance, but weaker than normal; 5 = Normal Strength). The MRC grades were rescored from 6 to 4 response options (0, paralysis; 1, severe weakness; 2, slight weakness; 3, normal strength) for the RT-MRC in order to acceptably fulfill Rasch model expectations. Sum scores range from 36 "normal" to 0 "quadriplegic".

Values and changes from Baseline in original MRC sum score and in RT-MRC sum score will be summarized by treatment group and for all participants and listed by treatment group at each scheduled assessment during the Treatment and Observation Period.

For the change from Baseline at each scheduled assessment during the Treatment and Observation Period, treatment differences will be compared using the same MMRM analysis as for the primary endpoint, with the fixed categorical effects of treatment group, assessment week (at pre-specified levels determined by the visit schedule), the treatment by week interaction and the route of administration of prior Ig therapy, as well as continuous fixed covariate of the Baseline value, and participant as a random effect. Analyses will be performed for the FAS utilizing the observed cases.

## 8.2.7 CIDP PRO and Fatigue scale

The **CIDP PRO instrument** consists of 2 domain scales;

- Pain Severity numeric rating scale
- Neuropathy scale.

Pain Severity consisting of 4 items assessing pain severity in the past 7 days and at the time of completion of the instrument, using 0-10 numeric rating scales. Summed total raw score will range between 0 to 40 with higher scores reflecting higher levels of pain severity.

The Neuropathy scale consists of 17 items rated within a 7-day recall period on a 6-point Likert severity scale ranging from “none” to “very severe”. The summed total raw score will range from 17 to 102 with higher scores reflecting higher levels of pain and physical sensations severity.

The **Fatigue instrument** consists of 3 domain scales; Physical Fatigue comprising 16 items; Mental Fatigue comprising 18 items and Fatigability comprising 21 items. All 55 items across the 3 domain scales are rated within a 7-day recall period on a 5-point Likert frequency scale ranging from “none of the time” to “all of the time”. The summed total raw scores for each of the 3 scales will range between 16 and 80; 18 to 90 and 21 to 105 points for the Physical, Mental, and Fatigability, scales respectively with a potential for an exploratory total overall score ranging from 55 to 275. Higher scores reflect higher levels of fatigue across all domain scale scores.

Values and changes from Baseline in CIDP-PRO instrument and in fatigue scores will be listed by treatment group at each scheduled assessment during the Treatment and Observation Period. Summary tables will be provided at an item level. If items are missing, the sum will be set to missing.

Following psychometric evaluation and refinement (eg, reduction in number of items) of these domain scales by using data generated in CIDP01, transformed interval 0-100 scoring will be provided for each domain score with higher scores reflecting higher levels of fatigue. A psychometric analysis plan will be created, which will detail all the exploratory and correlation analyses between the newly developed PROs and clinical variables. The PROs will also be participant to a Rasch analysis. The results of the psychometric analyses will be reported separately from the clinical study report (CSR). This analysis is not in scope of this SAP.

## 8.2.8 PGIS and PGIC

Participants will rate their global impression of CIDP symptom severity and fatigue severity respectively, on a 5-point Likert severity scale ranging from “none” to “very severe”.

Participants will rate their global impression of change (if at all) in CIDP symptom and fatigue respectively, on a 7-point Likert severity scale ranging from “very much improved” to “very much worse” from Baseline/start of clinical study treatment to the scheduled visits.

Frequencies of subjects scoring in the respective categories in Patient Global Impressions of Severity (PGIS) and changes in frequencies from Baseline will be presented via a shift table by visit per treatment group and listed by treatment group at each scheduled assessment during the Treatment and Observation Periods.

Patient Global Impressions of Change (PGIC) will be summarized via frequencies of each response by visit and treatment group and listed by treatment group at each scheduled assessment during the Treatment and Observations Periods.

### 8.2.9 Use of rescue medication

The percentage of participants with concomitant medication identified as rescue medication [Yes/No] in the eCRF and time to first rescue medication administration will be summarized by treatment group and for all participants and listed by treatment group at each scheduled assessment during the Treatment and Observation Period.

If a participant receives rescue medication at multiple times, the relative day of the first occurrence is used to define the time to rescue medication.

The statistical methods applied to use of rescue medication and time to use of rescue medication will be the same as for CIDP relapse (iRODS), see Sections 8.2.1 and 8.2.1.1. The rule for handling missing data is described in Section 4.2.7.

## 9 PHARMACOKINETICS AND PHARMACODYNAMICS

### 9.1 Pharmacokinetics

Pharmacokinetic variables of rozanolixizumab like AUC (area under the curve),  $C_{\max}$  (maximum concentration) cannot be derived, since blood sampling will be performed at 1 time point post-dosing per visit only. Thus, PK is restricted to concentration data.

Concentration data will be summarized for treatment rozanolixizumab by exposure (%) categories (see section 10.1) and time point using the number of available observations, mean, median, SD, minimum, maximum, geoMean, (and associated 95% confidence intervals), and geoCV (assuming log-normally distributed data) based on the PK-PPS.

Concentration data will be summarized for treatment rozanolixizumab by time point and █ status (6 classifications; see Section 9.3.2) using the number of available observations, mean, median, SD, minimum, maximum, geoMean, (and associated 95% confidence intervals), and geoCV (assuming log normally distributed data) based on the PK-PPS.

Individual concentrations of rozanolixizumab as well as planned and actual dose administered will be listed by treatment group for the SS and summarized for the PK-PPS, and will include the actual sampling time in days relative to the previous dose.

The following rules will apply for PK data listings and summaries:

- Values below the LLOQ will be reported as BLQ.
- Descriptive statistics of concentrations will be calculated if at most 33% of the individual data points at a timepoint are missing or are not quantifiable (<LLOQ). Values that are BLQ will be replaced by the numerical value of the LLOQ/2 in this instance. However, if  $n \leq 3$ , then only n, minimum and maximum will be presented as summary statistics. The other descriptive statistics will be left blank. If more than 33% of data points is missing then no summary statistics are given, irrespective of n.
- If no participants have data, only  $n=0$  will be presented. The other descriptive statistics will be left blank.
- The 95% CI lower and 95% CI upper should be left blank if the SD (or equivalently, the geoCV) is 0
- The geoCV will be calculated using the following formula where SD is the standard deviation from the log-transformed data

$$\text{geoCV (\%)} = \sqrt{[\exp(\text{SD}^2) - 1]} \times 100$$

For each participant, individual concentration versus time (week) profiles will be presented graphically in linear and semi-logarithmic scale. In addition, combined individual (spaghetti

plots) concentration versus time profiles will be presented in linear and semi-logarithmic scale with all participants overlaid on the same figure.

All figures will include the LLOQ on the semi-logarithmic plots.

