### **14.4.2 PK analyses**

Pharmacokinetic variables of rozanolixizumab like AUC (area under the curve),  $C_{\max}$  (maximum concentration) cannot be derived, since blood sampling will be performed at 1 time point post-dosing per visit only. Thus, PK is restricted to concentration data.

In contrast to the general descriptive display, concentration data will be summarized by treatment group, actual dose received, and time point using the number of available observations, mean,

median, SD, minimum, maximum, geometric mean (and associated 95% confidence intervals), and geometric coefficient of variation (assuming log-normally distributed data). Values below the lower limit of quantification (LLOQ) will be reported with a clear sign indicating that they were below the LLOQ. Descriptive statistics of concentrations will be calculated if at least two-thirds of the individual data points are quantifiable ( $\geq$ LLOQ). Individual concentrations of rozanolixizumab will also be displayed graphically.

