#### **14.4.3 PD analyses**

For all PD variables, descriptive statistics for the value, change from Baseline, and/or percentage change from Baseline will be tabulated by treatment group, actual dose received, and time point.

The PD variables will include serum IgG, IgG subclass, and neurofilament light chain concentrations.

Population PK analyses and PK/PD analyses may be conducted for the PD variables of interest. All such PK and PK/PD analyses will be described in a separate Data Analysis Plan (DAP) however results will not be reported in the CSR.

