Participants with the reduced dose due to tolerability issues will be mapped under the same treatment groups. These participants will be flagged in the listings. For the Observation period the same treatment groups will be displayed.

Data listings containing all documented data and all calculated data, as required for the variables and analysis applicable to the final analyses, will be generated.

The visit type information (home or site visit) will be included into the listings.

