## 10.1 Extent of exposure

Eligible participants will be randomized 1:1 to receive rozanolixizumab [REDACTED] or placebo. Randomized (intended) dose will be calculated based on participant's weight at screening as follows:

Randomized dose (mg)= weight at screening (kg)\*

The IMP solution contains [REDACTED] of rozanolixizumab. Actual dose in mg at Visit(i) will be calculated as follows:

Actual dose at Visit(i) (mg) = Total actual volume delivered at Visit(i) (mL) \* [REDACTED]  
where actual volume delivered is collected in eCRF, and in case of interruption it should be  
calculated as the sum of actual volumes delivered.

Overall exposure (%) will be calculated as mean exposure (%) at each visit as follows:

Overall exposure (%) =mean([Actual dose at Visit (i) (mg)/ Randomized dose (mg) - 1]\*100)

Overall exposure will be categorized as follows:

- $<-10\%$
- $\geq -10\%$  and  $\leq +10\%$
- $\geq +10\%$

The exposure categories will be used for the definition of the MFAS (Section 3.5.5) as well as for the representation of Pharmacokinetic data (Section 9.1).

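### SAP 9.1 groups rozanolixizumab concentrations by whole-treatment mean exposure, and SAP 9.2 has no dose split for PD, where the protocol plans summaries by actual dose received

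*SAP*

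**What the plan says.** Protocol 14.4.2: "concentration data will be summarized by treatment group, actual dose received, and time point". Protocol 14.4.3 says of all PD variables that descriptive statistics "will be tabulated by treatment group, actual dose received, and time point". In both sections Amendment 2 added actual dose received (Protocol 18.5, Changes #35 and #36). Its rationale says the descriptive analyses are meant to show which doses were really given.

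SAP 9.1: "Concentration data will be summarized for treatment rozanolixizumab by exposure (%) categories (see section 10.1) and time point". SAP 10.1 defines the measure behind these categories: "Overall exposure (%) will be calculated as mean exposure (%) at each visit as follows", followed by a formula that averages (actual dose / randomized dose - 1) × 100 over visits. The three classes are below -10%, from -10% to +10% inclusive, and +10% or more. SAP 10.1 says they serve both the MFAS and the PK tables.

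SAP 9.2.1 (total IgG and subclasses) and SAP 9.2.2 (NF-L) summarise by treatment group and time point, with no dose dimension. SAP 3.1: "Participants with the reduced dose due to tolerability issues will be mapped under the same treatment groups"; it adds that they are flagged in listings. SAP 3.9, on changes to protocol-defined analyses, mentions neither the PK grouping nor the missing PD split.

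**The concern.** Protocol 5.1, 6.4 and 7.2 allow an individual's dose to be reduced for tolerability during treatment. A by-time-point concentration table is useful if its rows say what dose lies behind the concentrations. A category fixed by the mean over all doses cannot do that once a dose has changed, because later infusions then decide the row in which earlier samples appear. Full-dose and reduced-dose samples from one participant always share a row.

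At stake are the descriptive PK tables and, because SAP 9.2 has no split at all, the tables for total IgG, which is a secondary objective (Protocol 3.2). No primary, safety or decision analysis uses the PK grouping.

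**Working it through.** **Inputs**
- 12 weekly doses, at Visits 2, 4, 6 and 8 to 16 (Protocol 7.2).
- Nominal levels of about 10 mg/kg and, when reduced, about 7 mg/kg. They are redacted in most places but legible in the Table 7-1 title in Protocol 18.5, Change #16, and in the continued heading of Table 7-2 in Protocol 7.2.
- PK samples: predose and 4 h postdose at Visits 2, 4, 6, 8 and 10; predose at Visits 12, 14 and 16; once at Visits 3, 5, 7 and 17 (Protocol Table 10-1).
- Assumption: all 12 doses are given, and a reduction, once made, continues.

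**1. The plan's own figure.** The Table 7-1 footnote says doses are within ±10% of intended except at 47 to 50 kg and 63 kg. The concentration is redacted, so it is an assumption here. The band spacing gives 14 kg/mL × 10 mg/kg = 140 mg/mL (Table 7-1) and 20 kg/mL × 7 mg/kg = 140 mg/mL (Table 7-2). At 140 mg/mL the whole-kg weights outside ±10% are exactly 47, 48, 49, 50 and 63. Among 120 to 160 mg/mL in steps of 5, no other value reproduces the footnote.

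**2. Nominal doses (no concentration needed).** One reduced dose deviates by (7/10 - 1) × 100 = -30%. With k of 12 reduced, overall exposure = -30k/12 = -2.5k%.
- k = 1 to 4: -2.5% to -10.0%. The participant stays in the ±10% class, and so do all samples taken after the reduction. At k = 4 (from Visit 13) these are Visit 14 predose, Visit 16 predose and Visit 17.
- k = 5 to 11: -12.5% to -27.5%. The participant is in the <-10% class, and so are all earlier full-dose samples. At k = 8 (from Visit 9, mean -20%) there are 10: Visit 2 postdose; Visit 3; Visit 4 pre and post; Visit 5; Visit 6 pre and post; Visit 7; Visit 8 pre and post.

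**3. Weight-band volumes at the assumed 140 mg/mL.** Overall exposure = [(12 - k)f + kr]/12, where f and r are the deviations at full and reduced volume.

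| Weight | Volumes | f | r | Largest k within ±10% | Mean at that k | Mean at k + 1 |
|---|---|---|---|---|---|---|
| 65 kg | 5 to 3 mL | +7.7% | -35.4% | 4 | -6.7% | -10.3% |
| 70 kg | 5 to 4 mL | 0% | -20% | 6 | -10.0% | -11.7% |
| 80 kg | 6 to 4 mL | +5% | -30% | 5 | -9.6% | -12.5% |

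At 70 kg, six reduced doses means reduction from Visit 11. Four samples then follow a reduced dose (predose at Visits 12, 14 and 16, and Visit 17), and all four sit in the ±10% class.

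The same dosing history can also be classified differently by weight. Four reduced doses give 4 × (-20)/12 = -6.7% at 70 kg. At 100 kg (7 to 5 mL; f = -2%, r = -30%) they give (8 × (-2) + 4 × (-30))/12 = -11.3%.

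**4. Grouping by the last infusion instead.** At 140 mg/mL every reduced dose is between -14.3% and -41.7% of intended, so every post-reduction sample falls below -10% at every weight. Full-dose samples fall within ±10% except at the footnoted weights.

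**The case against.** The strongest case against runs as follows.

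- **The label is accurate for what it names.** The SAP rows are classes of mean exposure; it defines no full-dose or reduced-dose row. This stands. A reader might infer that the table misstates its contents. It does not; it answers a different question from the one in Protocol 14.4.2.
- **Actual dose received is not defined in the protocol.** This stands. Taking it as the dose last given before the sample is a reading, though a natural one for a by-time-point table. Nor does it separate doses cleanly, since predose samples carry exposure from earlier infusions.
- **The data are recoverable.** SAP 9.1 lists individual concentrations with planned and actual dose and plots individual profiles, SAP 3.1 flags reduced-dose participants, and Protocol 14.4.3 allows separate PK/PD modelling. This mitigates. SAP 9.1 also says these data are summarised for the PK-PPS, but it defines no summary by dose.
- **SAP 1 defaults to the protocol where the SAP is silent.** For PD this might be said to keep the split alive, but SAP 9.2 specifies the layout without it. For PK the SAP specifies something else.
- **Protocol 7.2 says the dose stays constant.** That sentence follows the one on Screening weight and reads as concerning weight. If meant more widely, it must be reconciled with the reductions allowed in 5.1, 6.4 and 7.2 itself.
- **The effect may be small.** With 34/2 = 17 active participants in one row, a single misplaced participant lowers an arithmetic mean by at most 1/17, about 6%, even at zero concentration with the others equal. That is fair for the ±10% row; a sparse <-10% row has no such protection.

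A reader might also infer from the nonlinear exposure in Protocol 2 that pooling distorts concentrations by more than the dose ratio. The documents give no figure for that, and single-dose nonlinearity does not establish it for a pooled repeat-dose mean.

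**Conclusion.** The point holds as a wrong grouping rule for PK and an omitted split for PD, both departing from Protocol 14.4.2 and 14.4.3 without an entry in SAP 3.9. The averaging problem needs at least one participant whose dose is reduced during treatment. The documents do not say how many to expect, so no frequency can be attached. With no reduction, the classes mainly reflect weight-band rounding and incomplete infusions.

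For an affected participant the size is clear: at nominal doses, up to 4 of 12 reduced doses leave no trace in the category, and 5 or more move every earlier full-dose sample out of the ±10% class. The weight-specific limits (4 to 6 at 65 to 80 kg) rest on the inferred 140 mg/mL; the nominal result does not. All figures assume 12 doses given, because SAP 10.1 does not say whether a missed dose counts as zero in the mean. The consequence is confined to descriptive PK and PD tables.

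**What to change.** - **SAP 9.1:** group each concentration after the first dose by the actual dose level of the last infusion before the sample (or that infusion's own exposure category), by time point. Show Visit 2 predose separately. Dose level is the cleaner choice, since at the footnoted weights a full dose already lies outside ±10%.
- **SAP 9.2.1 and 9.2.2:** add the same actual-dose split for total IgG, IgG subclasses and NF-L.
- **SAP 10.1:** keep overall mean exposure for the MFAS only. Make the third class >+10%; as written, exactly +10% falls in two classes, whereas SAP 3.5.5 excludes only values above 10%.
- **SAP 3.9:** list any departure from Protocol 14.4.2 or 14.4.3 that remains.

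The cost is SAP wording and table programming; actual volume per visit is already in the eCRF (SAP 7 and 10.1). The downside is sparse reduced-dose cells: under SAP 9.1, n ≤ 3 shows only n, minimum and maximum. Predose samples will still carry some exposure from earlier doses, which a table footnote can state.
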